Trough FEV1 is defined as the average of FEV1 obtained 23 hours 15 minutes and 23 hours 45 minutes post-morning dose of the previous day; LSM = Least Square Mean; n = Number of subjects with at least one post baseline visit in the summarized category; The model will include trough FEV1 from all visits (Days 1, 6, 13, 20 and Day 21) and fixed terms for treatment, visit, center, baseline, treatment by visit and baseline by visit interactions; Unstructured covariance structure is used.

[figure not shown]
---

Programming notes: Font for text/label number = 10 pt;

---

Figure 14.2.1.6  
Plot of Change from Baseline in Day 21 Trough FEV1 (L)  
Dose Response Modelling (Non-Linear Model)

Full Analysis Set

Emax model with 3 parameters is used; n = Number of subjects on Day 21; Trough FEV1 is defined as the average of FEV1 obtained 23 hours 15 minutes and 23 hours 45 minutes post-morning dose of the previous day;

[figure not shown]
---

Programming notes: Font for text/label number = 10 pt

---

Figure 14.2.3.1  
Plot of Mean Plasma Concentrations by Day (Linear Scale)

PK Analysis Set  
Panel/Day: <Day 1, Day 21>

---

Programming notes: Font for text/label number = 10 pt;

Treatments (4 lines) should be overlaid.

[figure not shown]
Repeat for

Figure 14.2.3.2 Plot of Mean Plasma Concentrations by Day (Semi-Log Scale)  
Similar to Figure 14.4.1.1

---

PK Analysis Set  
Panel/Day: <Day 1, Day 21>

Figure 14.2.4.1  
Plot of Mean Amount of Urine Excreted by Day (Linear Scale)

[figure not shown]
---

Programming notes: Font for text/label number = 10 pt; Treatments (4 lines) should be overlaid.

---

Figure 14.2.4.2  
Plot of Mean Amount of Urine Excreted by Day (Linear Scale)

PK Analysis Set  
Panel/Day: <Day 1, Day 21>

---

[figure not shown]
Programming notes: Font for text/label number = 10 pt;

---

Figure 14.2.4.2  
Plot of Combined Individual Concentrations – Plasma

PK Analysis Set

Panel/Day/Treatment Group: <Day 1, Day 21> <treatment group>

[figure not shown]
---

Programming notes: Font for text/label number = 10 pt;

---

Figure 14.2.5.1  
Plot of Dose Proportionality - Plasma

Panel/Day/Parameter: <Day 1, Day 21> <parameter>

Programming notes: Font for text/label number = 10 pt;

Y-axis = Parameter (unit) =  $C_{maxSS}$  (day 21 only) ;  $AUC_{0-\tau SS}$  (day 21 only)

Repeat for

Figure 14.2.5.2 Plot of Dose Proportionality - Urine

Y-axis = Parameter (unit) =  $A_{etau}$  (day 1 and day 21)

Page XX of YY

Table 14.3.1.1  
 Overall Summary of Adverse Events

Safety Set

	GSP304					Spiriva R	
	(N=xxx) n (%) [#]	(N=xxx) n (%) [#]	(N=xxx) n (%) [#]	Total (N=xxx) n (%) [#]	Placebo (N=xxx) n (%) [#]	5 ug (N=xxx) n (%) [#]	Total (N=xxx) n (%) [#]
TEAEs	xx (xx.x) [#]	xx (xx.x) [#]	xx (xx.x) [#]	xx (xx.x) [#]	xx (xx.x) [#]	xx (xx.x) [#]	xx (xx.x) [#]
TEAEs Leading to Discontinuation [1]	xx (xx.x) [#]	xx (xx.x) [#]	xx (xx.x) [#]	xx (xx.x) [#]	xx (xx.x) [#]	xx (xx.x) [#]	xx (xx.x) [#]
TEAEs Related to Study Drug	xx (xx.x) [#]	xx (xx.x) [#]	xx (xx.x) [#]	xx (xx.x) [#]	xx (xx.x) [#]	xx (xx.x) [#]	xx (xx.x) [#]
AEs Leading to Withdrawal [2]	xx (xx.x) [#]	xx (xx.x) [#]	xx (xx.x) [#]	xx (xx.x) [#]	xx (xx.x) [#]	xx (xx.x) [#]	xx (xx.x) [#]
SAE	xx (xx.x) [#]	xx (xx.x) [#]	xx (xx.x) [#]	xx (xx.x) [#]	xx (xx.x) [#]	xx (xx.x) [#]	xx (xx.x) [#]
SAE Seriousness Reasons							
Congenital Anomaly or Birth Defect	xx (xx.x) [#]	xx (xx.x) [#]	xx (xx.x) [#]	xx (xx.x) [#]	xx (xx.x) [#]	xx (xx.x) [#]	xx (xx.x) [#]
Persistent or Significant Disability or Incapacity	xx (xx.x) [#]	xx (xx.x) [#]	xx (xx.x) [#]	xx (xx.x) [#]	xx (xx.x) [#]	xx (xx.x) [#]	xx (xx.x) [#]
Death	xx (xx.x) [#]	xx (xx.x) [#]	xx (xx.x) [#]	xx (xx.x) [#]	xx (xx.x) [#]	xx (xx.x) [#]	xx (xx.x) [#]
Initial or Prolonged Hospitalization	xx (xx.x) [#]	xx (xx.x) [#]	xx (xx.x) [#]	xx (xx.x) [#]	xx (xx.x) [#]	xx (xx.x) [#]	xx (xx.x) [#]
Medically Important Event	xx (xx.x) [#]	xx (xx.x) [#]	xx (xx.x) [#]	xx (xx.x) [#]	xx (xx.x) [#]	xx (xx.x) [#]	xx (xx.x) [#]
Life Threatening	xx (xx.x) [#]	xx (xx.x) [#]	xx (xx.x) [#]	xx (xx.x) [#]	xx (xx.x) [#]	xx (xx.x) [#]	xx (xx.x) [#]
SAEs Related to Study Drug	xx (xx.x) [#]	xx (xx.x) [#]	xx (xx.x) [#]	xx (xx.x) [#]	xx (xx.x) [#]	xx (xx.x) [#]	xx (xx.x) [#]

AE = Adverse Events; SAE = Serious Adverse Events; TEAE = Treatment-Emergent Adverse Events; TEAEs are defined as AEs (identified by PT) that begins or that worsens in severity after at least one dose of study treatment has been administered, up to the last study visit; PT = Preferred Term; n = Number of subjects reporting at least one TEAE in that category; [#] = Number of individual occurrences of the TEAE in that category

[1] counts all TEAEs leading to study discontinuation or treatment discontinuation during treatment period or follow-up period

[2] counts all AE leading to permanent discontinuation of study drug during treatment period or leading to withdrawal (study or drug discontinuation) from study during run-in, treatment period, or follow-up period

Program location/program name.sas/ddmmmyyyy/hh:mm  
Source Data: Listing xxxxxxx Database Extract Date: ddmmmyyyy

---

Programming notes:

---

Table 14.3.1.2  
 Summary of Treatment Emergent Adverse Events per SOC and PT

Safety Set

	GSP304					Spiriva R	
	(N=xxx)	(N=xxx)	(N=xxx)	Total (N=xxx)	Placebo (N=xxx)	5 ug (N=xxx)	Total (N=xxx)
	n (%) [#]	n (%) [#]	n (%) [#]	n (%) [#]	n (%) [#]	n (%) [#]	n (%) [#]
Any TEAE	xx (xx.x) [#]	xx (xx.x) [#]	xx (xx.x) [#]	xx (xx.x) [#]	xx (xx.x) [#]	xx (xx.x) [#]	xx (xx.x) [#]
SOC #1	xx (xx.x) [#]	xx (xx.x) [#]	xx (xx.x) [#]	xx (xx.x) [#]	xx (xx.x) [#]	xx (xx.x) [#]	xx (xx.x) [#]
PT #1	xx (xx.x) [#]	xx (xx.x) [#]	xx (xx.x) [#]	xx (xx.x) [#]	xx (xx.x) [#]	xx (xx.x) [#]	xx (xx.x) [#]
...	xx (xx.x) [#]	xx (xx.x) [#]	xx (xx.x) [#]	xx (xx.x) [#]	xx (xx.x) [#]	xx (xx.x) [#]	xx (xx.x) [#]
SOC #2	xx (xx.x) [#]	xx (xx.x) [#]	xx (xx.x) [#]	xx (xx.x) [#]	xx (xx.x) [#]	xx (xx.x) [#]	xx (xx.x) [#]
PT #2	xx (xx.x) [#]	xx (xx.x) [#]	xx (xx.x) [#]	xx (xx.x) [#]	xx (xx.x) [#]	xx (xx.x) [#]	xx (xx.x) [#]
...	xx (xx.x) [#]	xx (xx.x) [#]	xx (xx.x) [#]	xx (xx.x) [#]	xx (xx.x) [#]	xx (xx.x) [#]	xx (xx.x) [#]
...							

SOC = System Organ Class; PT = Preferred Term; Treatment Emergent AEs (TEAEs) are defined as AEs (identified by PT) that begins or that worsens in severity after at least one dose of study treatment has been administered, up to the last study visit; PT = Preferred Term; N = Number of safety subjects; n = Number of subjects reporting at least one TEAE in that category; [#] = Number of individual occurrences of the TEAE in that category

Program location/program name.sas/ddmmmyyyy/hh:mm

Source Data: Listing xxxxxxx Database Extract Date: ddmmmyyyy

Programming notes:

Ordered in terms of decreasing frequency for SOC, and PT within SOC, in the treatment group, and then alphabetically for SOC, and PT within SOC.

Repeat Table for:

Table 14.3.1.3 Summary of Treatment-Related Emergent Adverse Events per SOC and PT

Programming note: In the first row: Any Treatment-Related AE

Table 14.3.1.4 Summary of Pre-Treatment Adverse Events per SOC and PT

Footnote: Pre-Treatment AEs (PTAEs) are defined as AEs (identified by PT) that begin or that worsen in severity between study Day -14 and study drug

administration, and last up to the AE stop date

Programming note: In the first row: Any Pre-Treatment AE

Table 14.3.1.5 Summary of Serious Adverse Events per SOC and PT

Programming note: In the first row: Any Serious AE

Table 14.3.1.6 Summary of Serious Adverse Events Leading to Study Discontinuation per SOC and PT

Programming note: In the first row: Any Serious AE Leading to Study Discontinuation

Table 14.3.1.7 Summary of Treatment-Related Emergent Serious Adverse Events per SOC and PT

Programming note: In the first row: Any Treatment-Related Serious AE

Table 14.3.1.8 Summary of Treatment Emergent Adverse Events Leading to Study Discontinuation per SOC and PT

Programming note: In the first row: Any TEAE Leading to Study Discontinuation

---

Table 14.3.1.9  
 Summary of Treatment Emergent Adverse Events by Severity per SOC and PC

Safety Set

Category	GSP304					Spiriva R	
	(N=xxx)	(N=xxx)	(N=xxx)	Total (N=xxx)	Placebo (N=xxx)	5 ug (N=xxx)	Total (N=xxx)
	n (%) [#]	n (%) [#]	n (%) [#]	n (%) [#]	n (%) [#]	n (%) [#]	n (%) [#]
Any TEAE	Any	xx (xx.x) [#]	xx (xx.x) [#]	xx (xx.x) [#]	xx (xx.x) [#]	xx (xx.x) [#]	xx (xx.x) [#]
	Mild	xx (xx.x) [#]	xx (xx.x) [#]	xx (xx.x) [#]	xx (xx.x) [#]	xx (xx.x) [#]	xx (xx.x) [#]
	Moderate	xx (xx.x) [#]	xx (xx.x) [#]	xx (xx.x) [#]	xx (xx.x) [#]	xx (xx.x) [#]	xx (xx.x) [#]
	Severe	xx (xx.x) [#]	xx (xx.x) [#]	xx (xx.x) [#]	xx (xx.x) [#]	xx (xx.x) [#]	xx (xx.x) [#]
SOC #1	Any	xx (xx.x) [#]	xx (xx.x) [#]	xx (xx.x) [#]	xx (xx.x) [#]	xx (xx.x) [#]	xx (xx.x) [#]
	Mild	xx (xx.x) [#]	xx (xx.x) [#]	xx (xx.x) [#]	xx (xx.x) [#]	xx (xx.x) [#]	xx (xx.x) [#]
	Moderate	xx (xx.x) [#]	xx (xx.x) [#]	xx (xx.x) [#]	xx (xx.x) [#]	xx (xx.x) [#]	xx (xx.x) [#]
	Severe	xx (xx.x) [#]	xx (xx.x) [#]	xx (xx.x) [#]	xx (xx.x) [#]	xx (xx.x) [#]	xx (xx.x) [#]
PT #1	Any	xx (xx.x) [#]	xx (xx.x) [#]	xx (xx.x) [#]	xx (xx.x) [#]	xx (xx.x) [#]	xx (xx.x) [#]
	Mild	xx (xx.x) [#]	xx (xx.x) [#]	xx (xx.x) [#]	xx (xx.x) [#]	xx (xx.x) [#]	xx (xx.x) [#]
	Moderate	xx (xx.x) [#]	xx (xx.x) [#]	xx (xx.x) [#]	xx (xx.x) [#]	xx (xx.x) [#]	xx (xx.x) [#]
	Severe	xx (xx.x) [#]	xx (xx.x) [#]	xx (xx.x) [#]	xx (xx.x) [#]	xx (xx.x) [#]	xx (xx.x) [#]
...							
SOC #2	Any	xx (xx.x) [#]	xx (xx.x) [#]	xx (xx.x) [#]	xx (xx.x) [#]	xx (xx.x) [#]	xx (xx.x) [#]
	Mild	xx (xx.x) [#]	xx (xx.x) [#]	xx (xx.x) [#]	xx (xx.x) [#]	xx (xx.x) [#]	xx (xx.x) [#]
	Moderate	xx (xx.x) [#]	xx (xx.x) [#]	xx (xx.x) [#]	xx (xx.x) [#]	xx (xx.x) [#]	xx (xx.x) [#]
	Severe	xx (xx.x) [#]	xx (xx.x) [#]	xx (xx.x) [#]	xx (xx.x) [#]	xx (xx.x) [#]	xx (xx.x) [#]
PT #2	Any	xx (xx.x) [#]	xx (xx.x) [#]	xx (xx.x) [#]	xx (xx.x) [#]	xx (xx.x) [#]	xx (xx.x) [#]
	Mild	xx (xx.x) [#]	xx (xx.x) [#]	xx (xx.x) [#]	xx (xx.x) [#]	xx (xx.x) [#]	xx (xx.x) [#]
	Moderate	xx (xx.x) [#]	xx (xx.x) [#]	xx (xx.x) [#]	xx (xx.x) [#]	xx (xx.x) [#]	xx (xx.x) [#]
	Severe	xx (xx.x) [#]	xx (xx.x) [#]	xx (xx.x) [#]	xx (xx.x) [#]	xx (xx.x) [#]	xx (xx.x) [#]
...							

SOC = System Organ Class; PT = Preferred Term; TEAE = Treatment-Emergent Adverse Events; TEAEs are defined as AEs (identified by PT) that begins or that worsens in severity after at least one dose of study treatment has been administered, up to the last study visit; PT = Preferred Term; N = Number of safety subjects; n = Number of subjects reporting at least one TEAE in that category; [#] = Number of individual occurrences of the TEAE in that category;

Each subject is counted once within each System Organ Class and Preferred Term according to the maximum intensity for all TEAEs within that System Organ Class, High Level Term or Preferred Term.

Program location/program name.sas/ddmmmyyyy/hh:mm

Source Data: Listing xxxxxxx Database Extract Date: ddmmmyyyy

---

Programming notes:

Ordered in terms of decreasing frequency for SOC, and PT within SOC, in the treatment group, and then alphabetically for SOC, and PT within SOC.

---

Table 14.3.1.10  
 Summary of Treatment Emergent Adverse Events by Relationship to Study Treatment per SOC and PC

Safety Set

Category	GSP304				Spiriva R		
	(N=xxx) n (%) [#]	(N=xxx) n (%) [#]	(N=xxx) n (%) [#]	Total (N=xxx) n (%) [#]	Placebo (N=xxx) n (%) [#]	5 ug (N=xxx) n (%) [#]	Total (N=xxx) n (%) [#]
Any TEAE	Not Related xx (xx.x) [#]	xx (xx.x) [#]	xx (xx.x) [#]	xx (xx.x) [#]	xx (xx.x) [#]	xx (xx.x) [#]	xx (xx.x) [#]
	Related xx (xx.x) [#]	xx (xx.x) [#]	xx (xx.x) [#]	xx (xx.x) [#]	xx (xx.x) [#]	xx (xx.x) [#]	xx (xx.x) [#]
SOC #1	Not Related xx (xx.x) [#]	xx (xx.x) [#]	xx (xx.x) [#]	xx (xx.x) [#]	xx (xx.x) [#]	xx (xx.x) [#]	xx (xx.x) [#]
	Related xx (xx.x) [#]	xx (xx.x) [#]	xx (xx.x) [#]	xx (xx.x) [#]	xx (xx.x) [#]	xx (xx.x) [#]	xx (xx.x) [#]
PT #1	Not Related xx (xx.x) [#]	xx (xx.x) [#]	xx (xx.x) [#]	xx (xx.x) [#]	xx (xx.x) [#]	xx (xx.x) [#]	xx (xx.x) [#]
	Related xx (xx.x) [#]	xx (xx.x) [#]	xx (xx.x) [#]	xx (xx.x) [#]	xx (xx.x) [#]	xx (xx.x) [#]	xx (xx.x) [#]
...							

SOC = System Organ Class; PT = Preferred Term; TEAE = Treatment-Emergent Adverse Events; TEAEs are defined as AEs (identified by PT) that begins or that worsens in severity after at least one dose of study treatment has been administered, up to the last study visit; PT = Preferred Term; N = Number of safety subjects; n = Number of subjects reporting at least one TEAE in that category; [#] = Number of individual occurrences of the TEAE in that category

Program location/program name.sas/ddmmmyyyy/hh:mm

Source Data: Listing xxxxxxx Database Extract Date: ddmmmyyyy

Programming notes:

Table 14.3.2  
Listing of Deaths for All Causes

All Screened Subjects

Site/Subject ID	Study Period	Treatment	Treatment Start Date	Date of Death	Reason for Death
xxxxxx	Screening	NA	NA	ddmmmyyyy	xxx

NA = Not Applicable

program location/program name.sas/ddmmmyyyy/hh:mm

---

Programming notes:

---

Table 14.3.4.1

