### **9.6.3. Exploratory Analysis**

If appropriate, a dose response model will be fitted to the primary endpoint to estimate the dose response relationship. Dose response models to be evaluated will include  $E_{max}$  (3-parameter) and linear models.

The  $E_{max}$  model will be fitted as follows:

$$\text{Endpoint} = E_0 + \frac{E_{max} \text{ Dose}}{\text{Dose} + ED50} + \varepsilon$$

where  $E_0$  = Response at dose 0,  $E_{max}$  = Maximum effect,  $ED50$  = Dose at which 50% of the maximum effect is reached and  $\varepsilon$  = Residual error.

The linear model will be fitted as follows:

$$\text{Endpoint} = E_0 + \beta \text{Dose} + \varepsilon$$

where  $E_0$  = Response at Dose 0,  $\beta$  = slope and  $\varepsilon$  = Residual error

Should these models not fit the data appropriately other models may be explored. For all of the models, baseline will be included as a covariate at  $E_0$ . However, baseline may be fitted at  $ED50$  or  $E_{max}$  for the  $E_{max}$  model depending on how the model fits the data best. Other covariates will be explored. Depending upon the adequacy of model fitting some parameters may need to be parameterized on the log scale (e.g. variance,  $ED50$ ,  $E_{max}$ ). The most appropriate model will be assessed visually, by evaluating the AIC and by looking at the residuals. To build confidence in the chosen model, the null model:

$$\text{Endpoint} = E_0$$

will also be fitted to the data and the p-value from a likelihood ratio test will be computed; i.e. the change in deviance (-2 Log Likelihood) between the chosen model and the null model will be compared to a chi-squared distribution with degrees of freedom equal to the difference in the number of parameters in the two models.

Dose response model parameter estimates, along with corresponding 95% confidence intervals, from the final dose response model will be presented.

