[1] Change from baseline in FEV1 is modeled using a categorical dose as an explanatory variable with visit and visit by dose interaction as fixed effects. The model will include trough FEV1 from all visits (Days 1, 6, 13, 20 and Day 21) and fixed terms for treatment, visit, center, baseline, treatment by visit and baseline by visit interactions; Unstructured covariance structure is used.

[2] Change from baseline in FEV1 is modeled using a continuous dose as an explanatory variable with visit and visit by dose interaction as fixed effects.

Program location/program name.sas/ddmmmyyyy/hh:mm

Source Data: Listing xxxxxxx Database Extract Date: ddmmmyyyy

Programming notes:

Table 14.2.1.8  
Exploratory Statistical Analysis of Change from Baseline in Day 21 Trough FEV1 (L)  
Dose Response Modelling (Non-Linear Model)

Full Analysis Set

	Parameter	Estimate(SE)	CI
E-Max Mode 1 [1]	Intercept	xx.x (xx.xx)	(xx.x, xx.x)
	Parameter 1	xx.x (xx.xx)	(xx.x, xx.x)
	Parameter 2	xx.x (xx.xx)	(xx.x, xx.x)

[1] Non-linear model using a continuous dose as an exploratory variable on change from baseline in FEV1 will be analyzed using an E-max model with 3 parameters; n = Number of subjects on Day 21. Trough FEV1 is defined as the average of FEV1 obtained 23 hours 15 minutes and 23 hours 45 minutes post-morning dose of the previous day.

Intercept = E0, the response at dose = 0 (placebo response)

parameter 1 = Emax, the maximum change in the response compared to placebo

parameter 2 = ED50, the dose at 50% of maximum change in the response compared to placebo (ED50)

The estimate of the ED50, the minimum effective dose has to be chosen close to twice the ED50 to obtain 100% of the maximum change in the response compared to placebo.

Program location/program name.sas/ddmmmyyyy/hh:mm

Source Data: Listing xxxxxxx Database Extract Date: ddmmmyyyy

---

Programming notes:

---

Table 14.2.3.1  
 Summary of Plasma Concentration (pg/mL) on Day 1 and Day 21 by Subject

PK Analysis Set

Panel/Day/Treatment Group: <Day 1, Day 21> <treatment group>

Subject ID	pre-dose	2 min	4 min	6 min	10 min	15 min	30 min	45 min	60 min	75 min	90 min
XXX-XXXX	XX.X										
XXX-XXXX	XX.X										
.....											
n	XX										
Mean	XX.X										
SD	XX.XX										
Median	XX.X										
Min; Max	XX.X;XX.X										
%CV	XX.X										
GM	XX.X										

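### The footnote to the Emax table credits about twice the ED50 with 100% of the maximum effect; the SAP's own equation gives 66.7% there and never reaches 100%

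*SAP*

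**What the plan says.** Section 9.6.3 (Exploratory Analysis) plans, if appropriate, to fit a linear model and a three-parameter Emax model to the primary PD endpoint. The Emax equation is Endpoint = E0 + Emax × Dose/(Dose + ED50) + error. E0 is the response at dose zero, and ED50 is defined as "Dose at which 50% of the maximum effect is reached". There is no Hill exponent.

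The shell for Table 14.2.1.8 (section 12.2, non-linear dose-response model) carries the same model: its footnote says that change from baseline in FEV1 "will be analyzed using an E-max model with 3 parameters". It defines the parameters in the same way, with Emax being "the maximum change in the response compared to placebo". The footnote then ends with a rule for reading the result: "the minimum effective dose has to be chosen close to twice the" ED50 "to obtain 100% of the maximum change in the response compared to placebo".

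The term minimum effective dose appears nowhere else in the SAP.

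**The concern.** The footnote doubles the dose that gives half the effect and concludes that this gives the whole effect. That would be right if the effect rose in a straight line from zero through the ED50 point. The Emax curve bends over instead and approaches its maximum without reaching it.

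Characterising the dose response is one of the two primary objectives in section 3.1.1. The rest of section 9.6.3 deals with choosing and fitting the model; only this sentence tells the reader what a fitted ED50 implies about dose, and it is worded as a directive. Printed under the estimates, it could lead a reader to credit a dose with the full effect when the table's own model gives two thirds of it.

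The sentence also attaches the name minimum effective dose to a dose said to deliver the maximum effect. The SAP does not define the term and sets no target effect from which such a dose could be derived.

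**Working it through.** **Inputs, all from the SAP**
- Model (section 9.6.3): Endpoint = E0 + Emax × Dose/(Dose + ED50).
- Same three-parameter model and parameter definitions in the footnote to Table 14.2.1.8.
- Dose named in the footnote: about 2 × ED50.
- Share of the maximum change that the footnote attaches to it: 100%.

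**Formula.** Write Dose = r × ED50. The share of the maximum effect is

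(Endpoint − E0)/Emax = Dose/(Dose + ED50) = r × ED50/(r × ED50 + ED50) = r/(r + 1).

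E0, Emax and ED50 all cancel, so the redacted dose levels are not needed.

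**Check against the SAP's own definition.** At r = 1 the share is 1/2 = 50%, which agrees with the definition of ED50.

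**The footnote's figure.** At r = 2 the share is 2/3 = 66.7%, not 100%. The footnote's figure is not reproduced.

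| Dose as a multiple of ED50 | Share of Emax |
|---|---|
| 1 | 50% |
| 2 | 66.7% |
| 4 | 80% |
| 9 | 90% |
| 19 | 95% |
| 99 | 99% |

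Solving r/(r + 1) = 1 requires r = r + 1, which has no solution, so no finite dose reaches 100%.

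**Readings that might rescue the sentence**
- *Close to* twice rather than exactly twice: r from 1.8 to 2.2 gives 1.8/2.8 = 64.3% to 2.2/3.2 = 68.8%.
- A sigmoid Emax model with Hill exponent h, which the SAP does not specify: the share at r = 2 is 2^h/(2^h + 1), that is 80.0% for h = 2, 88.9% for h = 3 and 97.0% for h = 5. None reaches 100%.
- Baseline as a covariate on E0, ED50 or Emax, or parameters on the log scale, both allowed in section 9.6.3: for given parameter values the share is still r/(r + 1).
- Straight-line extrapolation: 2 × 50% = 100%. This does reproduce the footnote's figure, but it is not the Emax model. The linear model has its own table (14.2.1.7), and as written in section 9.6.3 it has neither a maximum nor an ED50.

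**Size in mL, as an illustration only.** The SAP does not state a value for Emax. If it were 150 mL, borrowing the planning difference in section 4.3.1, the model would give 150 × 2/3 = 100 mL at twice the ED50, where the footnote implies 150 mL.

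**The case against.** The strongest counter-argument concerns weight, not correctness. The Emax fit is labelled exploratory, is done only if appropriate, and may give way to another model. The primary PD inference comes from the MMRM contrasts of each dose with placebo (sections 9.4 and 9.6.1). No estimate, confidence interval, test, analysis set or sample size depends on the footnote, and the body of the SAP never repeats the rule. Section 6.2 lets footnotes be modified after the data analyses, so the sentence might not survive into the report. A reader who has the printed parameters, the equation in section 9.6.3 and the planned Figure 14.2.1.6 could see the mistake.

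All of that stands, and it is why the point ranks below anything that touches the primary analysis. It does not make the sentence right. Section 6.2 permits changes to footnotes but does not commit anyone to changing this one, and a rule for reading ED50 is better settled before ED50 is known.

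Two further cautions are fair. The 150 mL figure equates the model's asymptote with a planning difference, which the SAP does not do, so the percentages are the finding. And a summary of the dose for a chosen target effect would be an added analysis, not something needed to remove the contradiction.

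**Conclusion.** The concern holds. For the three-parameter Emax model that both section 9.6.3 and Table 14.2.1.8 specify, twice the ED50 corresponds to 66.7% of the maximum effect, and 100% is not attained at any finite dose. The footnote's 100% is too high by one third of Emax. This is algebra from the SAP's own equation; it rests on no outside source, no redacted value and no assumption about the fitted parameters beyond a non-zero Emax and a positive ED50.

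The practical consequence is confined to interpretation of an exploratory table. It deserves correction because the dose response is a primary objective and this is the only interpretive rule the SAP attaches to the fitted curve. The point concerns the model arithmetic alone and takes no position on which dose should be chosen.

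**What to change.** Reconcile the footnote to Table 14.2.1.8 with section 9.6.3 before unblinding. Deleting the last sentence is enough. If some guidance on reading ED50 is wanted, replace it with what the equation gives: fraction of Emax = Dose/(Dose + ED50).

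Optionally, if the team wants an effective-dose summary, it could define the term, pre-state a target difference from placebo, and report the corresponding dose from the fitted curve with a 95% confidence interval. That is an addition, not part of the correction.

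The correction changes one footnote and leaves data, model and estimates untouched.
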